1.3. Summary of the potential risk and benefits to human subjects

Study subjects will not receive any direct therapeutic benefit from taking part in this study.

The subjects enrolled in the present study being healthy are not expected to derive any benefit from participating in the present study. DF2755A is being developed for a chronic condition, IC/BPS, that as of today lacks effective treatment. A growing body of evidence suggest that molecules affecting the IL-8 – CXCR1/2 axis like DF2755A could represent a novel treatment options. DF2755A exhibits a non-clinical safety and pharmacokinetic profile compatible with chronic treatment, and therefore satisfies all criteria to qualify as a candidate for clinical studies in patients with IC/BPS. As to the present phase I clinical trial, adequate safety margins based upon toxicology studies in rats and dogs, a staggering approach to dosing subjects at each dose level, close monitoring of clinical conditions of participants and a safety monitoring committee to be convened between each dose level to review the data of the previous cohort and confirm or select the next dose for evaluation, represent adequate safety measures to ensure the safety of trial participants.

1.4. Description and justification for the dosage regimen

Doses were calculated using the body surface area conversion. The calculated maximum recommended starting dose (MRSD) is 117 mg in rats and 130 mg in dogs. Based on data available for the rat, the proposed MRSD is 50 mg/subject, 23 times lower than the HED at NOAEL. As general rule the human equivalent efficacy dose is higher than the efficacy dose obtained in animals.

A prediction of the human PK parameters and the human equivalent pharmacological dose of DF2755A using allometric scale simulation has been carried out using the information on efficacy in rats.

Pharmacologic HED was calculated using the estimated (scaled) human clearance and the AUC that resulted in pharmacological activity. Pharmacologic HED ranged from 77 to 3202 mg BID (i.e. 144 -6404 mg) depending on the rat efficacious exposure and projected CL used. Considering these results, the dose of 50 mg could be considered the suitable first dose in human due to the fact that it is lower than the projected human pharmacological equivalent dose by a factor >7 or >10 if 7 or 10 mg/kg are considered the efficacy doses in rats, respectively.

These results are in agreement, see above, with the HED calculated from the 4-week oral toxicity study in rat were applying a safety factor of 23-fold the starting dose results to be 50 mg.

To preserve the safety of the subjects after the first cohort (PK parameters permitting) a PK simulation to determine the predicted PK parameters at the higher dose/s will be performed to predict the expected exposure.

The following single doses are planned to be administered in Part A:

Table 8: Doses for administration in Part A

Proposed Doses		SAD		
Human Equivalent dose (HED) considering the more sensitive species (RAT) mg/kg	Dose mg/subj (60kg)	Dose mg/kg	Safety margin	Ratio
19.44	50	0.83	23.33	
	150	2.50	7.78	3
	450	7.50	2.59	3
	700	11.67	1.67	1.55

The maximum dose of 700 mg is in the range of the pharmacological HED and it is in the range of the exposure covered by the toxicological studies.

The first MAD cohort will be initiated only after the authorization, from ANSM of a substantial amendment that will be presented in order to notify the results of SAD part of the study.

The anticipated doses tested in Part B are the following:

Table 9: Doses for administration in Part B

Proposed Doses		MAD (proposed 14 days) b.i.d.			
Human Equivalent dose (HED) considering the more sensitive species (RAT) mg/kg	Dose mg/subj (60kg)	Total dose day mg/subj	Dose mg/kg	Safety margin	Ratio
19.44	100	200	3.33	5.83	
	200	400	6.67	2.92	2
	300	600	10.00	1.94	1.5

The administered dose in part B could be modified according to the results of the part A.

1.5. Ethical considerations

The study will be performed according to the local regulations, the recommendations on Good Clinical Practice (GCP) "ICH Topic E6, CPMP/ICH/135/95", July 1996 including post Step 4 errata, status September 1997 and post Step errata (linguistic corrections), July 2002 and according to the relevant guidelines of the Declaration of Helsinki.

Dose Calculation: Guidance for Industry - Estimating the Maximum Safe Starting Dose in Initial Clinical Trials for Therapeutics in Adult Healthy Volunteers - U.S. Department of Health and Human Services - Food and Drug Administration - Center for Drug Evaluation and Research (CDER) July 2005

The clinical study will start upon receipt of the approval of both the Ethics Committee “Comité de Protection des Personnes” (CPP) and the French Health Authorities “Agence Nationale de sécurité du médicament et des produits de santé” (ANSM).

1.6. Description of the population to be studied

Part A: Eight healthy male and female subjects (6 active and 2 placebo) will be included in the four dose level. At least two healthy female subjects will be included in each cohort. One of them should be allocated to placebo. . In total, 32 subjects will be enrolled.

Part B: Twelve healthy male and female subjects (9 active and 3 placebo) will be included in each dose level. Between three and six healthy female subjects will be included in the cohort. At least one of them should be allocated to placebo. .

In total, 36 subjects will be enrolled.

For both parts, subjects will be recruited from volunteers' database of the clinical unit. Newspaper advertisements, radio spots, posters, mailing, specific press inserts, broadcast message or clinical unit recruitment website may be used. Only study-specific recruitment tools approved by EC will be used.

2. STUDY OBJECTIVES AND PURPOSE

2.1. Principal objective

To evaluate the tolerability and safety of ascending single and repeated doses of DF2755A in healthy adult male and female volunteers.

2.2. Secondary objectives

- To determine the pharmacokinetics parameters of DF2755A
- To establish a dose concentration-response relationship over a wide range of doses in order to select a narrower range of doses and dosing regimen to be subsequently studied in patients after single and multiple administration
- To evaluate the effects of ascending single and repeated doses on the pharmacodynamics parameters.
- To compare metabolites pathway in human with the one observed in animals

3. STUDY DESIGN

3.1. Evaluation criteria

3.1.1. Primary endpoint

AE, vital signs, 12-lead ECG, laboratory exams.

3.1.2. Secondary endpoints

Measurement of pharmacokinetics parameters: C_{max} , t_{max} , λ_z , $t_{1/2}$, AUC_{0-last} , AUC_{inf} , V_z/F , CL/F , Ae_{0-last} , CL_R , total amount in faeces, parent:metabolite(s) ratio.

Measurement of Cytokine Inflammation Markers [CXCL1(Gro alfa), CXCL2(Gro beta); CXCL5(ENA-78), CXCL6 (GCP-2), CXCL8 (IL-8)] in part B and Leukocyte subsets (CD11b and CD18) in part A, except for 1st cohort and part B.

3.2. Design

The study is a phase I, single center, double-blind, placebo controlled, randomized, ascending single and repeated doses study in healthy male and female volunteers.

The design consists of a double blind comparison of the test compound versus placebo in which the dose is increased in successive treatment periods.

The Multiple Ascending Dose (MAD) has to be started only after the end of all the cohorts of Single Ascending Dose (SAD). Besides in order to decide to move forward from SAD to MAD, the pharmacokinetic data for all doses administered during SAD will be evaluated (i.e. plasma: quantitative determination of DF2755A bound and unbound; qualitative and preliminary quantitative determination of known metabolites; urine and faeces: qualitative and quantitative determination of parent compound and qualitative and preliminary quantitative investigation of known metabolites).

Dose will be escalated in order to achieve enough safety information on an interval of doses possibly encompassing both the effective dose and the maximum tolerated dose (defined as the highest t dose devoid of any clinical signs/symptoms).

Part A: Single doses of 50 mg oad, 150 mg oad, 450 mg oad or 700 mg oad of DF2755A are planned to be tested in healthy volunteers.

[figure not shown]
Part B: Repeated doses of 100 mg bid, 200 mg bid or 300 mg bid of DF2755A are planned to be tested in healthy volunteers.

The study plan is shown in Figure 7 and 8.

Study procedures are detailed in Section 6 and 7.

Figure 7 - Study plan - Part A

D-21	D-2	D-1	D1	D2	D3	D4
	→					→
	Selection					
Ambulatory Visit		Arrival to the center	Treatment Administration	Hospitalisation	Departure from the center	

Figure 8 - Study plan - Part B

3.3. Description of the measures taken to minimize and avoid bias

3.3.1. Randomization

The randomization list will be provided by Eurofins Optimed.

The randomization list will be prepared to permit that one of the two first subjects treated per each cohort, will receive a placebo.

The treatments will be allocated at D1 for both parts.

3.3.2. Blinding

The following measures are taken to avoid bias:

- Double Blind Study,
- The capsule containing active drug and placebo will be indistinguishable in appearance.

3.3.3. Risk assessment, study conduct and method of dose escalation

3.3.3.1. Number of subjects receiving the study drug simultaneously

Based on clinical data, no major specific safety issues related to acute toxicity with DF2755A is expected at the doses planned to be tested. However, to mitigate the risk, the administration of the investigational product within each dose group cohort will be conducted according to a staggering approach. For the 2 first subjects of a dose level, the administrations will take place with a lag time of 1h during which the Investigator will carefully monitor for adverse events (AEs) or reactions, if any. For the subsequent subjects of a dose level the administrations will take place with a lag time of 30 minutes.

For example: for Part A: 2 subjects on the first day, 3 subjects on the second day, and the remaining 3 subjects on the third day. And for Part B: 2 subjects on the first day, 3 subjects on the second day, 3 subjects on the third day, and the remaining 4 subjects on the fourth day.

3.3.3.2. Dose Escalation

The dose escalation is designed to progress from the first to the highest dose up to the occurrence of relevant events supporting Maximal Tolerated Dose (MTD) determination.

At the end of each dose level, an interim safety report will be issued by the Investigator. A dose escalation teleconference meeting will be held between the Investigator and the Sponsor representatives, and the decision on how to proceed (e.g. next higher dose) will be taken on the basis of a blind safety and pharmacokinetic data review.

The following safety parameters will be reviewed for both part, for all the subjects:

- Any adverse events reported;
- All laboratory parameters outside of ranges;

- Concomitant therapy;
- Physical examination abnormalities;
- Vital signs abnormalities;
- ECG abnormalities.

For dose escalation, Pharmacokinetic data on plasma (quantitative determination of DF2755A bound and unbound; qualitative and preliminary quantitative determination of known metabolites), urine and faeces recovery (qualitative and quantitative determination of parent compound and qualitative and preliminary quantitative investigation of known metabolites) will be considered by using, for each new dose level, the pharmacokinetic results of the previous dose level in order to re-estimate the safety margin based on the animal-human exposure ratio. This re-estimation must be taken into account when deciding whether to proceed to the next dose level.

The exposure does not exceed the AUC of 1000 $\mu\text{g}\cdot\text{h}/\text{mL}$.

Identification of non-acceptable risks or significant proportion of AEs with common pathological pattern can justify the modification of the dose escalation design.

After mutual agreement between the Sponsor and the Investigator and if it is considered useful for the selection of the next dose level, the treatment of a specific subject and/or a cohort may be unblinded before the next dose level of DF 2755A is administered.

At the end of the teleconference meeting, the following decisions can be taken:

- Dose escalation will continue as scheduled;
- An intermediate dose between the current dose and the following dose will be administered to the next cohort;
- A lower intermediate dose, between the current dose and the dose administered in the previous cohort will be administered to the next cohort;
- The current dose will be repeated in the next cohort;
- The study will be stopped.

According to the conclusion of this meeting, the formal agreement/disagreement to move to a next cohort will be signed by both the Sponsor and the Investigator.

3.4. Expected duration of subject participation

3.4.1. Description and duration of trial periods

Part A:

Screening within 21 days prior to the first administration,
Hospitalization approximately for 4 days (D-1 morning to D4 morning). Consideration should be given to the hospitalization after the last dose, in fact it could be reviewed according to PK parameters of the compound after each dose of SAD.

Expected duration: approximately 4 weeks for each participating subject.

Part B:

Screening within 21 days prior to the first administration,
Hospitalization approximately for 17 days (D-1 morning to D17 morning). Consideration should be given to the hospitalization after the last dose, in fact it could be reviewed according to PK parameters of the compound after each dose of MAD.

Expected duration: approximately 6 weeks for each participating subject.

3.4.2. Duration of follow-up

During the last visit, subjects will undergo a complete clinical and biological examination, identical to the examination at the start of the study. AEs will be recorded, and if they are on-going a further follow-up will be arranged; follow-up will continue until the event is resolved or the condition is unlikely to change or the subject is lost to follow-up (see section 8.5).

3.5. Stopping rules

3.5.1. Stopping rule applicable at any time

In case of occurrence of a SAE at least possibly related to the study drug administration, the safety review committee will decide to put the study on hold, and will ask for unblinding for the subject. If the subject was treated by placebo, the study will be continued as planned per protocol. If the subject was receiving DF2755A, the study will be immediately interrupted and depending on the nature and SAE resolution it should be potentially re-started after submission and approval by both EC and CA of a substantial amendment.

3.5.2. Stopping rule for a subject

During the treatment period, the safety and tolerability will be evaluated on an ongoing basis, the following criteria will apply to stop a subject:

- The subject experiences an AE that prevents him from continuing in the study,
- Significant increase (i.e. $> 3N$) of ALT (N being the upper limit of the normal value),
- Abnormal laboratory results with simultaneous increases of total bilirubin ($> 2 N$), ALT ($> 2 N$) and alkaline phosphatases ($> 1.5 N$),
- The subject develops a serum creatinine ≥ 2 times the ULN,
- Sustained QTcF value of > 500 msec confirmed by at least one repeat ECG,
- The subject withdraws consent,
- At the request of the Sponsor or at the Investigator's request (for example if the Investigator considers that the subject's health is compromised by remaining in the study or the subject is not sufficiently cooperative).

See also Section 3.6 "Removal of Subjects from Therapy or Assessment".

3.5.3. Stopping rules within a group

During the treatment period, the safety and tolerability will be evaluated on an ongoing basis, the following criteria will apply to stop the cohort :

- 2 subjects experiencing severe non serious AEs considered as at least possibly related to the study drug,
- 2 subjects experiencing a significant increase (i.e. $> 5N$) of ALAT (N being the upper limit of the normal value),

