3.5.4. Stopping rule for dose escalation

The safety review committee will decide to stop the dose escalation as planned per protocol in case of occurrence of:

- 2 subjects experiencing severe non serious AEs of the same organ class and nature related to the study drug,
- 4 subjects (for SAD) and 8 subjects (for MAD) experiencing study drug related moderate non serious AEs (that are considered directly related to the drug effect unless they resolved despite the continuation of the treatment),
- 2 subjects of the group experience a significant increase (i.e. $> 3 N$) ALAT,
- 2 subjects of the group experience simultaneous increases of total bilirubin ($> 2 N$), ALAT ($> 2 N$) and alkaline phosphatases ($> 1.5 N$),

- 2 subjects has a sustained QTc value > 500 ms (confirmed by a second ECG under strict resting position),
- One subject presents a C_{max} or $AUC_{(0-24h)}$ values respectively above 150 $\mu\text{g}/\text{mL}$ and 1000 $\mu\text{g}/\text{mL} \cdot \text{h}$,
- The mean C_{max} and $AUC_{(0-24h)}$ leads to believe taking into account the dose increase that C_{max} or $AUC_{(0-24h)}$ values of 125 $\mu\text{g}/\text{mL}$ and 600 $\mu\text{g}/\text{mL} \cdot \text{h}$ will be overpass with the following planned higher dose,
- In MAD part the mean at the steady state C_{max} and $AUC_{(t)}$ leads to believe taking into account the dose increase that C_{max} or $AUC_{(0-24h)}$ values of 125 $\mu\text{g}/\text{mL}$ and 800 $\mu\text{g}/\text{mL} \cdot \text{h}$ will be overpass with the following planned higher dose,

In one of the cases listed above, the dose group in progress will be stopped and the blind could be broken. Regarding laboratory and QTc abnormalities described above, if unblinding confirms that at least two subjects presenting these abnormalities were receiving the active drug the dose escalation will be stopped.

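### One cohort stop has two ALAT thresholds (5N in 3.5.3, 3N in 3.5.4), and a cohort stop for unlike severe adverse events carries no stated hold on dose escalation

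*Protocol*

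**What the plan says.** Protocol 3.5.2 stops an individual subject on "Significant increase (i.e. $> 3N$) of ALT (N being the upper limit of the normal value".

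Protocol 3.5.3 has two bullets, each of which stops the cohort:
- For ALAT: "2 subjects experiencing a significant increase (i.e. $> 5N$) of ALAT"
- For severe events, with no condition on organ class: "2 subjects experiencing severe non serious AEs considered as at least possibly related to the study drug"

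It does not mention escalation.

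Protocol 3.5.4 concerns escalation. Its list includes:
- For ALAT: "2 subjects of the group experience a significant increase (i.e. $> 3 N$) ALAT"
- For severe events, now with a matching condition: "2 subjects experiencing severe non serious AEs of the same organ class and nature related to the study drug"

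Its closing paragraph then reaches back to the current cohort: "In one of the cases listed above, the dose group in progress will be stopped and the blind could be broken". For laboratory and QTc findings, the further step of ending escalation is conditional: "if unblinding confirms that at least two subjects presenting these abnormalities were receiving the active drug the dose escalation will be stopped".

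Under Protocol 3.3.3.2, after each dose level "the decision on how to proceed (e.g. next higher dose) will be taken on the basis of a blind safety and pharmacokinetic data review". Continuing on schedule is one of the outcomes it lists. Sponsor and Investigator may agree to unblind a subject or cohort before the next dose, and both must sign before the next cohort starts. Protocol 3.7.2 lets the Sponsor open a cohort's code only once the joint blinded decision has been made.

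**The concern.** There are two separate problems.

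First, the section that site staff would naturally open for a cohort stop gives 5N. The next section stops the same cohort at 3N. A stopping rule for healthy volunteers should give one number for one action.

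Second, 3.5.3 deliberately casts a wider net for severe events than 3.5.4 does: any organ class, and at least possible causality. When the wider net catches something that the narrower one does not, the cohort stops and the rules say nothing more. The next dose could then be chosen after a tolerability halt without anyone being obliged to learn whether the affected subjects had received drug. Safety is the primary objective, and for a related serious event 3.5.1 already provides a study hold and a request to unblind. The step just below that level has no counterpart.

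**Working it through.** The plan gives no error rate or operating characteristic for these rules, so there is no figure to reproduce. The check compares triggers and consequences, then does three short calculations.

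**1. ALAT nesting.** Let m be the second-highest ALAT multiple of N seen so far in a cohort.
- 3.5.3 fires when m > 5.
- 3.5.4 fires when m > 3.
- m > 5 implies m > 3, so 3.5.4 always fires no later than 3.5.3.

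Because the closing sentence of 3.5.4 attaches the cohort stop to each listed case, the 5N bullet adds nothing when both sections are applied. A grid of paired values agrees: no pair met 5N without meeting 3N, and 96 pairs met 3N without meeting 5N.

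**2. The band in laboratory units.** The laboratory ranges attached to the SAP give upper limits of 42 U/L (men) and 31 U/L (women).
- Men: 3 × 42 = 126; 5 × 42 = 210 U/L.
- Women: 3 × 31 = 93; 5 × 31 = 155 U/L.

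Two subjects inside these bands stop the cohort under 3.5.4 but not under 3.5.3.

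**3. Severe events side by side.**

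| | 3.5.3 | 3.5.4 |
|---|---|---|
| Number of subjects | 2 | 2 |
| Severity | severe, non-serious | severe, non-serious |
| Organ class and nature | any | must match |
| Causality | at least possible | related |
| Stated result | cohort stops | escalation and current group stop |

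Two events that meet the left column and do not match in class and nature fall outside the right one. The only text left is 3.3.3.2. It applies after every dose level whether or not a rule has fired, its review is blinded unless the parties agree otherwise, and it can end in the planned next dose.

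**4. What the treatment codes could add.** Assume no drug effect, so that the two affected subjects are a random pair from the cohort.
- Part A (6 active, 2 placebo): both on active = C(6,2)/C(8,2) = 15/28 = 54%; at least one on placebo = 46%.
- Part B (9 active, 3 placebo): both on active = C(9,2)/C(12,2) = 36/66 = 55%; at least one on placebo = 45%.

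These figures show how far a blinded review leaves allocation open under that assumption. They are not a risk estimate.

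**5. Side effect of unblinding.** Protocol 3.3.1 puts one placebo subject among the first two dosed in each cohort. Opening the code of one of that pair therefore reveals the other's treatment.

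**The case against.** **On ALAT.** Two tiers may have been intended: an automatic cohort stop at 5N, and a committee decision on escalation at 3N. The heading of 3.5.4 and its opening reference to the safety review committee fit that reading. The 3.5.4 list also includes exposure forecasts for the next planned dose, where stopping the current group makes little sense, so the loose text may be its closing sentence rather than the 5N bullet. This stands as a plausible account of intent, and the fix allows for it. It does not remove the conflict, because the closing sentence stops the dose group without qualification.

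A reader might also infer that subjects between 3N and 5N, or their cohort, would go on being dosed. The documents do not support that: 3.5.2 stops the individuals at 3N and 3.5.4 stops the group. Extra dosing would need someone to ignore 3.5.4.

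**On escalation.** Silence never leads to a higher dose. Section 3.3.3.2 requires a review and both signatures, and 1.3 describes a committee between dose levels. Section 3.3.3.2 also ties escalation to events that bear on the maximum tolerated dose, which 3.2 defines as the highest dose free of clinical signs or symptoms, and lets unacceptable risk justify a change. Section 4.4.2.2 lets the Investigator suspend the research. A blinded review can weigh the nature and timing of events, or simply assume active drug. All of this stands, so it would be wrong to infer that escalation proceeds automatically. But each of these safeguards is discretionary or general. None is triggered by a 3.5.3 stop, and none requires the codes of the affected subjects to be opened.

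Nor does 3.7.2 forbid unblinding before the decision. Section 3.3.3.2 allows it by mutual agreement and 3.5.4 foresees it. The 3.7.2 sentence merely sits awkwardly beside them.

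**Conclusion.** Both parts hold, at modest size.

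The ALAT bullet in 3.5.3 is redundant if 3.5.4 is followed and contradictory if 3.5.3 is read alone. It affects results in the 126–210 U/L (men) and 93–155 U/L (women) bands. On its own it changes no dosing when the protocol is applied as a whole.

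The missing hold is the more substantive part. After a cohort stop for two unlike severe events, what protects the next cohort is a discretionary review, blinded by default, rather than a rule. The documents give no rate for severe events or for ALAT elevations, so no frequency is claimed. The 54% and 55% figures rest on the no-effect assumption and the planned 6:2 and 9:3 allocation. The existing review and signatures keep this short of a critical defect, but it is worth correcting.

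**What to change.** 1. In 3.5.3, change the ALAT bullet to two subjects above 3N, in line with 3.5.2 and 3.5.4. If two tiers were meant, leave 5N and limit the closing sentence of 3.5.4 so that the 3N case does not stop the current group.
2. Add to 3.5.3: *Any cohort stop under this section suspends dose escalation until the case has been reviewed with the treatment of the affected subjects unblinded.* The narrower 3.5.4 rule for ending escalation stays as it is.
3. Add a cross-reference in 3.7.2 so that its restriction on opening codes before the blinded decision does not block this review. The same sentence keeps the Investigator blind to the end of the study, so the cross-reference should say who sees the opened codes.

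The cost is a few sentences of wording, with no change to sample size, visits or analyses. They can go into the substantial amendment that is already required before Part B; covering Part A would need an earlier one. In conduct, the price is an occasional pause and loss of the blind for the affected subjects. If one of the first two subjects dosed is affected, the other is in effect unblinded too, so the text should not promise that all other codes stay closed.
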